- 3. Vu and Goldberg et al. reported on the first 115 Uphold subjects. Defining failure as C > 0, and Aa > 0, they found short-term failure rates of 0%-4.2%, depending on the group, with total 2.6% mesh exposure rates. Anatomic failure rates, mesh erosion rates, dyspareunia rates, and patient satisfaction rates are very encouraging. [27] They reported on 47 women undergoing repair for vault prolapse using Uphold who had recurrence rates ranging from 0% in those with prior hysterectomy to 4.2% in those undergoing concurrent hysterectomy. The rate of mesh exposure was 3/115 (2.6%), including two in women with concurrent hysterectomy. Self-reported dyspareunia was more common preoperatively (13.4%) than postoperatively (9.3%). PFDI scores improved in all domains, and 93% of those who completed the Surgical Satisfaction Questionnaire (SSQ) reported they were satisfied and would choose the surgery again. [27]
- 4. Jirschele K et al. reported on 99 patients who underwent bilateral sacrospinous hysteropexy with polypropylene mesh in a multi-center, prospective trial followed to 12 months. The composite outcome revealed success of 97%. The overall mesh erosion rate was 6.52% and the overall reoperation rate was 7%. [28]
- 5. Letouzey et al. reported on 115 subjects with a minimum of 12-month follow-up and mean follow-up of 23 months. Of note, only 13 subjects (11%) had prior hysterectomy and 19 subjects (17%) had concomitant hysterectomy leaving the remaining 83 subjects undergoing mesh hysteropexy. The anatomical success rate was 93% with a patient satisfaction rate of 95%. The reoperation rate for mesh complications was 3.4%. [29]

A review of clinicaltrials.gov reveals that there are ongoing registered trials studying the Elevate procedure in hysteropexy and vault prolapse:

- The Sacrocolpopexy versus vaginal mesh procedure for pelvic prolapse is a randomized controlled trial with 60 participants. This study is ongoing but not recruiting patients.
- A prospective safety and efficacy cohort study of Elevate-AA prolapse repair system compared to native tissue repair for pelvic organ prolapse repair. The estimated enrollment is 494 and part of the FDA 522 study requirements.

Published Studies on Anterior/Apical Elevate:

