- Retreatment for prolapse (surgery or pessary), or
- 3. Any prolapse measure (Ba, C, Bp) is beyond the hymen (i.e. > 0 cm).

Bothersome vaginal bulge symptoms = positive response to Question 3 of the PFDI-20: Do you usually have a bulge or something falling out that you can see or feel in your vaginal area? and any degree of bother (i.e. any response other than "not at all" to the question "How much does this bother you?")

L.2. Secondary Outcome Measures

Secondary Aim 1 – Secondary Efficacy Outcomes: These measures will require a statistical analysis plan and will be reported in the primary outcome manuscript.

- Anatomic: POP-Q point (Aa, Ap, Ba, Bp, C) mean or median (but should be normally distributed)
 - (a) Measures postop in each group
 - (b) Proportion of participants in each group with C > -2/3 TVL
 - (c) Maximum extent of prolapse (defined as leading edge of prolapse Ba, C, Bp)

2. Functional:

- (d) Prolapse
 - (i) Patients Global Impression of Improvement (PGI-I) [49]
 - (ii) Mean overall prolapse symptoms using POPDI-6 scores (sub-scale of PFDI-20) [50]
- (e) Urinary
 - (i) Duration of postop catheterization
 - (ii) Mean UDI-6 scores (sub-scale of PFDI-20) [50]
 - (iii) De novo voiding dysfunction rates
 - (iv) De novo incontinence rates
 - 1. Stress
 - 2. Urge
 - 3. Mixed
- (f) Sexual/Body Image

- 1. Mean PISQ-IR [51] and BIPOP scales [52]
- 2. Rates of de novo dyspareunia
- (g) Bowel bowel function using CRADI-8 scores [50]
- (h) QOL
 - (i) General SF-12 scores and sub-scales [53]
 - (ii) Pelvic QOL mean PFIQ score [50]
 - (iii) Katz ADL (ref) (baseline only)
 - (iv) Functional Activity Scale (ref)
- Regret/Satisfaction:
 - (i) Regret with Decision Regret Scale (DRS-PFD) [54]
 - (j) Satisfaction with Decision Scale (SDS-PFD) [54]

Secondary Aim 2 – Safety: These measures will require a statistical analysis plan and will be reported in the primary outcome manuscript.

- Intraoperative safety: group comparisons of mean operative time, estimated blood loss, blood transfusion, intra- and postoperative complications categorized using a modification of the Dindo Classification. [55]
- 2. Adverse events mesh-related complications: mesh exposure in the vagina or mesh erosion into another organ and the classification of the intervention:
 - (a) None or non-surgical medical intervention only
 - (b) Minor or intra-office surgical intervention
 - (c) Outpatient surgery
 - (d) Inpatient surgery
- 3. Other complications possible in all arms:

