Appendix B-3: PPAR Inventory: Adverse Symptoms and Events for PPAR Capture

Adverse Symptoms	Description	PPAR Questions for Adverse Symptoms	Comments
Vaginal discharge		1. Frequency – (How often do you experience?) 2. Severity – (At its worst, how severe?) 3. Impact – (How much did it interfere with your usual activities?)	
De novo vaginal bleeding	New onset or persistent vaginal bleeding beyond 6 weeks.		
Pelvic pain	Any pain associated with worsening bother compared to preop occurring in the lower abdomen or genital area beyond 12 weeks postoperatively (excluding neuromuscular pain and dyspareunia).		
Dyspareunia	Any new onset pain associated with sexual activity that was not present during sexual activity preoperatively (AE = Anything other than Never).		
Stress urinary incontinence			
Urgency incontinence Fecal incontinence			
Constipation (new or worsening)	New onset or worsening condition in which medical treatment is required.		
Difficulty emptying bladder (new or worsening)	The new onset or worsening inability to completely empty the bladder during urination.		
Symptomatic mesh exposure (vaginal bleeding, problems with sexual relations etc.)			
Neurovascular event related to surgery	Numbness/weakness		

Adverse Events	Description	PPAR Questions for Adverse Events	Comments
Vaginal infection	Infection of the vagina determined by a physician using clinical or radiologic indicators to be uncommon to vagina and requiring treatment.	1. Severity 2. Impact	
Lower urinary tract infection (UTI)	UTI based on clinical judgment or confirmation of a culture proven by lab criteria also includes empiric antibiotic treatment for symptoms thought to be secondary to UTI.		*If UTI meets criteria for recurrent UTI, then "recurrent UTI" becomes the event.
Other infection* (specify)	Infection diagnosed using clinical or radiologic indicators not including vaginal infection, lower urinary tract infection, pelvic infection/abscess or infection/inflammation of bone.		
Laparoscopic/robotic port site hernia			
Emergency department visit for intervention related complication			
Intraoperative or perioperative event that changed management	Cautery burn, corneal abrasion, retained foreign body, ureteral or bladder injury requiring additional surgery, conversion to open surgery, ileus, bowel obstruction, need for blood transfusion.		Should capture MI, PE, CHF, as well as more minor things if they changed management.

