#### 3.2 Outcomes

The **primary outcome** for the study is treatment failure at any point greater than 6 weeks after the participant leaves the operating room; note that per protocol requirements, the patient cannot leave the operating room as a treatment failure. A participant will be considered a treatment failure if any ONE of the following criteria is met:

- 1) Report of bothersome vaginal bulge symptoms (see definition below), or
- 2) Re-treatment for prolapse (surgery or pessary), or
- 3) Any prolapse measure (Ba, C, Bp) is beyond the hymen (i.e. >0 cm)

Bothersome vaginal bulge symptoms = positive response to Question 3 of the PFDI-20: Do you usually have a bulge or something falling out that you can see or feel in your vaginal area? AND any degree of bother.

Participants not considered a treatment failure for the primary outcome will be considered a treatment success.

A number of **secondary outcome measures** will be used to support the analyses for the secondary aims listed earlier. Outcomes that will be used in the planned analyses in the primary ASPIRE manuscript associated with each of the secondary aims include:

- 1. Anatomical measures of treatment efficacy in the two treatment arms obtained at 6-month intervals after surgery:
  - a. Mean and median POPQ point location measures postoperatively in the two treatment arms.
  - b. Proportion of participants in each group with C > -2/3 TVL
  - c. Mean Median values of the maximum extent of prolapse (defined as leading edge of prolapse-Ba, C, Bp)
- 2. Functional measures of treatment efficacy in the two treatment arms as obtained from the measurement at 6 weeks as well as those at 6 months post-surgery and every subsequent 6-month time period through 5 years post surgery:
  - a. Participant impression of overall prolapse improvement at 6-month post-operative intervals as measured by Patients Global Impression of Improvement (PGI-I),
  - b. Mean overall prolapse symptoms at 6-month post-operative intervals based on POPDI-6 scores, and the overall PFDI total score .
  - c. Urinary function measured at 6-month post-operative time points using:
    - i. Mean UDI-6 scores
    - ii. Risk of de novo voiding dysfunction

- iii. Risk of de novo incontinence (stress, urge, and mixed)
- d. Sexual functional measures obtained at 6-month post-operative time points including:
  - i. PISQ-IR scale measures
  - ii. Risk of de novo dyspareunia

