Indicator of sexually active denovo dyspareunia**	PISQ-IR	Binary	surgery through 3 years	At each timepoint among women who were sexually active (PISQ-IR Q1: 1=yes) at baseline and at the timepoint's corresponding attended post-operative visit, based on the response to the PISQ-IR question Q11 "How often do you feel pain during sexual intercourse? " at baseline and the timepoint's corresponding attended post-operative visit, the indicator is defined as follows:
				1 = Yes, if a response of 1=never or 2=rarely is reported at baseline and a response of 3=sometimes, 4=usually, or 5=always is

				reported at the timepoint's corresponding attended post-operative visit 0 = No, else if there is a non-missing response reported at baseline and at the timepoint's corresponding attended post-operative visit . = Missing, otherwise
Indicator of not sexually active denovo dyspareunia**	PISQ-IR	Binary	surgery through 3 years	At each timepoint among women who were not sexually active (PISQ-IR Q1: 2=no) at baseline and at the timepoint's corresponding attended post-operative visit, based on the response to the PISQ-IR question Q2e asking if pain is a reason for not being sexually active at baseline and the timepoint's corresponding attended post-operative visit, the indicator is defined as follows:
				1 = Yes, if a response of 3=somewhat disagree or 4=strongly disagree is reported at baseline and a response of 1=strongly agree or 2=somewhat agree is reported at the timepoint's corresponding attended post- operative visit
				0 = No, else if there is a non-missing response reported at baseline and at the timepoint's corresponding attended post-operative visit
				. = Missing, otherwise
Indicator of dyspareunia	CRF-13, CRF-96	Binary	surgery through 3 years	Through the timepoint of follow-up, based on the Adverse Event Log (CRF-96) or specific complications as reported on the coordinator follow-up CRF-13 collected in 6-month intervals through 3 years, the indicator is defined as follows:

				1 = Yes, if denovo dyspareunia, worsening dyspareunia, or dyspareunia preventing intercourse is reported as evident (i.e. response of "AE", "SAE") on any of the complication tables as described above or "Dyspareunia" in the term reported in the AE log.

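### The two PISQ-IR de novo dyspareunia indicators omit, at each visit, women who have stopped sexual activity because of pain, and keep women with baseline pain in the denominator

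*SAP*

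**What the plan says.** De novo dyspareunia is a named secondary outcome in both documents: "Rates of de novo dyspareunia" in Protocol L.2 and "Risk of de novo dyspareunia" in SAP 3.2. SAP 9.3 gives three dyspareunia variables.

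- **Active women (PISQ-IR Q11, frequency of pain at intercourse).** Defined "among women who were sexually active (PISQ-IR Q1: 1=yes) at baseline and at the" post-operative visit. Yes means never or rarely at baseline and sometimes or more often at the visit.
- **Inactive women (PISQ-IR Q2e, pain as a reason for inactivity).** Defined "among women who were not sexually active (PISQ-IR Q1: 2=no) at baseline and at the" post-operative visit. Yes means disagreement at baseline and agreement at the visit.
- **Complication and adverse event indicator (CRF-13 and the AE log).** Yes if any of "denovo dyspareunia, worsening" dyspareunia or dyspareunia preventing intercourse is reported through 3 years. It has no condition on sexual activity.

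In both PISQ-IR indicators, No is assigned "else if there is a non-missing response reported at baseline and at the" visit, that is, to every remaining pair of answers. Dyspareunia results from the PISQ-IR are on the list of potential displays (SAP 14, eTable 4).

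**The concern.** Two features of the PISQ-IR definitions work against a de novo rate.

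First, inclusion depends on activity status at the follow-up visit. Stopping intercourse can be a consequence of the harm being measured. Q2e records whether pain is the reason, but the SAP uses that answer only for women who were already inactive at baseline. If arms differ in how many women stop because of pain, the PISQ-IR rows do not count those women as events. Randomisation does not protect a comparison among women selected on a post-surgery status.

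Second, a woman with pain at baseline cannot become a de novo case, yet she counts as a No. The protocol's own description of its dyspareunia item in Appendix B-3 is "Any new onset pain associated with sexual activity that was not present during sexual activity preoperatively". SAP 9.5.2 estimates binary outcomes as risk differences, which is the scale that this dilution affects.

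**Working it through.** The plan gives no figure to reproduce. The check applies the SAP 9.3 rules literally and then looks at what they do to a rate.

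**Inputs**
- Activity and coding rules: SAP 9.3.
- b = 13.4%: self-reported preoperative dyspareunia in an Uphold series cited in Protocol B.1.c. Its denominator is not stated, and the series includes hysteropexies.
- b = 10%, 30% and 50%, a 20% rate and a 10-point risk difference: assumed, to show the range.

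**Step 1. Who is covered at a visit**

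| Baseline | Visit | Indicator |
|---|---|---|
| active | active | active-women indicator |
| active | inactive | neither |
| inactive | active | neither |
| inactive | inactive | inactive-women indicator |

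Two of the four patterns fall outside both. The second row contains the women who stopped because of pain. The omission is per visit: a woman left out at one visit can count at another.

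**Step 2. Who is coded No**
- Q11 has 5 × 5 = 25 answer pairs. Yes: 2 × 3 = 6. No: 19, of which 3 × 5 = 15 have baseline pain.
- Q2e has 4 × 4 = 16 answer pairs. Yes: 2 × 2 = 4. No: 12, of which 2 × 4 = 8 have baseline pain.

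These are counts of answer patterns, not of women.

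**Step 3. Effect of the denominator.** Let r be the rate among women without baseline pain and b the share with baseline pain among women in the indicator at that visit.

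Reported rate = r × (1 − b). With equal b in two arms, reported risk difference = true difference × (1 − b), and (1 − b) cancels in a ratio.

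| b | r = 20% reported as | 10-point difference reported as |
|---|---|---|
| 10% (assumed) | 18.0% | 9.0 points |
| 13.4% (cited series) | 0.20 × 0.866 = 17.3% | 8.7 points |
| 30% (assumed) | 14.0% | 7.0 points |
| 50% (assumed) | 10.0% | 5.0 points |

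**Step 4. Effect of the activity condition.** Among women active and pain-free at baseline, let a be the proportion active with new pain at the visit, s_p the proportion who stopped because of pain and s_o the proportion who stopped for other reasons. Leave baseline-pain women aside.

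- SAP rule: a / (1 − s_p − s_o)
- Counting stopping because of pain, all women in the denominator: a + s_p
- The same, without women who stopped for other reasons: (a + s_p) / (1 − s_o)

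Under the SAP rule s_p enters only through the denominator and never as an event. The third rate minus the first has the sign of

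(a + s_p)(1 − s_p − s_o) − a(1 − s_o) = s_p(1 − s_p − s_o − a) ≥ 0,

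so the SAP rate is never above the third, and the factor (1 − b) only lowers it further. It can lie on either side of the second: with s_p = 0 and s_o > 0, a / (1 − s_o) exceeds a. The documents give no values for a, s_p or s_o, so this step yields a direction against one version of the rate but no size.

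**The case against.** The strongest reply is that women who stop because of pain are not lost to the trial. The CRF-13 and AE-log indicator counts dyspareunia preventing intercourse, with no activity restriction, at 6-monthly visits through 3 years. Protocol N.4 separately makes new or worsening dyspareunia that prevents intercourse an important complication to be compared between groups, and Protocol L.2 ties de novo and worsening dyspareunia under safety to the AE survey. This stands. A reader might infer from the PISQ-IR rows that the plan misses such women altogether, and the documents do not support that. What remains is that the complication indicator, as defined, pools de novo with worsening dyspareunia, so no planned row gives a de novo-only rate that includes women who stopped.

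A second reply is that a proportion among all assessed women is a legitimate quantity. This also stands in part. A reader might argue that the word risk in SAP 3.2 itself requires an at-risk denominator. It does not: the safety list in the same section, which includes de novo dyspareunia, measures risk as a proportion of participants. The case for the narrower denominator is that it is easier to interpret. Baseline pain precedes surgery, so keeping these women does not in itself create selection bias.

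Third, both PISQ-IR rows carry a double asterisk whose footnote is not visible in the text available. It might qualify the population or the denominator. That is a limit on this point, not a fault in the plan.

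**Conclusion.** The point holds for the two PISQ-IR indicators and for the de novo-only rate. At each visit they leave out women who changed activity status, including those who stopped because of pain, and they count women with baseline pain as No.

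The denominator effect is a factor of (1 − b): about 13% in relative terms at b = 13.4%, and more if baseline pain is commoner here than in the cited series. Equal b across arms, on which the unchanged ratio depends, is an assumption: b is taken among women who meet the activity condition at the visit, not among all women randomised.

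The effect of the activity condition on the comparison between arms cannot be sized. A reader might infer a known bias for or against one operation. The documents give no rates of stopping by arm, so neither its size nor its direction between arms is established.

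These outcomes are secondary and descriptive, without multiplicity control (SAP 7.7 and 9.5.1), and no primary conclusion depends on them. The change should be made because it is cheap and gives a clearer safety-relevant rate. Confidence is medium, because the CRFs and the footnote are not visible.

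**What to change.** 1. Restrict the PISQ-IR de novo denominators to women without baseline pain: Q11 never or rarely if active, Q2e disagree if inactive.
2. Among women active and pain-free at baseline, count as an event either active at the visit with Q11 sometimes or more often, or inactive at the visit with Q2e agree.
3. Show that rate with and without women who stopped for other reasons (Q2e disagree) in the denominator.
4. Keep the two existing strata as breakdowns, and leave the CRF-13 and AE-log indicator as it is.
5. Label the re-derivation post hoc if it is done after unmasking. SAP 12 (Version 2) already gives primary-outcome event counts by arm, so the label would apply now.

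The cost is programming only, since Q1, Q11 and Q2e are already collected. The downside is that the combined rate joins two different PISQ-IR items, a pain frequency and a reason for inactivity. A table note should say so, and the stratum breakdowns let the reader separate them.

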## **9.4** Primary Analysis Methods

The primary analysis is conducted on a modified intent-to-treat population for tests of superiority and the Per Protocol population for tests of non-inferiority. Because there were some treatment switchers during surgery, some switchers are removed from populations to maintain conservative and interpretable evaluations. See section 5. for definitions of populations, and details about which specific population is primary and supportive for the 4 primary hypotheses.

# **9.4.1** Primary Efficacy Outcome

The primary efficacy outcome is the time to surgical failure and is evaluated using all the data collected through the last operated subject's 3-year visit (primary endpoint). Since enrollment spanned 3 years, the duration of follow-up for some subjects included in the primary analysis is 5 years (60 months). Specifically, among subjects who experience a surgical failure, time to surgical failure is defined as the number of months (i.e. 6, 12, 18, 24, 30, 36, 42, 48, 54, or 60 months as intended by the 6-month interval visit schedule through a maximum of 5 years) from surgical intervention to first surgical failure at any post-operative visit 6 months through a maximum of 5 years after surgery.

Though surgical failure status is recorded at the 6-weeks post-operative visit, this data is not analyzed as these measures are collected too close to the date of surgical intervention. Instead, all subjects who attended the 6-week post-operative visit (i.e. 1.5 months) will be considered as not surgical failures at this visit. Subjects without a surgical failure at the end of follow-up are censored at their last attended visit.

A participant will be considered a surgical failure at the post-surgical visit if any ONE of the following criteria is met:

- Retreatment failure: retreatment for prolapse (surgery or pessary)
- Anatomic failure: prolapse beyond the hymen
- Symptomatic failure: bothersome vaginal bulge symptoms

Based on the definition of the primary outcome, the primary analytic approach will utilize a survival model to evaluate differences in time to surgical failure between the surgical arms.

Supporting numbers for survival analysis will be presented, including the number censored in each surgical arm in each period (from model-based approach described below) as well as the median, 25th, and 75th percentile for follow-up time in months for each surgical arm.

# 9.4.2 Primary Efficacy Analysis: Model-Based Survival Analysis

This model-based approach will serve as the primary analytic method for testing the comparative efficacy of the three strategies for uterovaginal prolapse as it can control for study design and potentially confounding variables. To appropriately account for the interval censored and right censored nature of the primary outcome data, and potential violation of the proportional hazards assumption across the entire follow-up time, while controlling for study design and potentially confounding variables in assessing intervention effects, a piecewise exponential (PWE) survival model will be employed. The PWE survival model is a model in which the time scale is divided into *K* periods and the underlying hazard function, h(t), is assumed to be constant within each period such that  $h(t) = \lambda_k \exp(\beta \mathbf{X})$ , where  $\lambda_k$  is the hazard function for period *k*, and **X** is a matrix of explanatory

variables with vector  $\beta$  coefficients (Breslow 1974). This piecewise approach effectively eliminates the need to specify the distribution of the hazard function and satisfies the proportional hazards assumption if the underlying hazard is constant within each period.

Among subjects who experience a surgical failure, the time to surgical failure (primary outcome) will be interval censored (i.e. lower bound, upper bound where both bounds are non-missing and lower bound < upper bound). Subjects who do not experience a surgical failure will be right censored (i.e. non-missing lower bound and missing upper bound) at their last attended visit. Specifically, the censoring interval for implementation in interval censored analysis will be defined as follows:

- lower bound = number of months (i.e. months as intended the by visit schedule) from the surgical intervention to the *last attended visit where the subject was considered to be not a surgical failure* across all post-operative visits starting at the 6 month visit. As such, subjects who were surgical failures at the 6-month post-operative visit will have a lower bound of 1.5 months corresponding to the 6-week post-operative visit. Based on this definition, the lower bound for the primary endpoint of 3 to a maximum of 5 years can take any of the following values 1.5, 6, 12, 18, 24, 30, 36, 42, 48, 54, or 60 months.
- upper bound = number of months (i.e. months as intended by the visit schedule) from the surgical intervention to *first post-operative visit with surgical failure* across all attended post-operative visits starting at the 6 month visit. As such, subjects who do not experience a surgical failure through the endpoint, will have a missing upper bound and will be right censored at their lower bound. Based on this definition, the upper bound for the primary endpoint of 3 to a maximum of 5 years can take any of the following values 6, 12, 18, 24, 30, 36, 42, 48, 54, or 60 months.

